- Option 2: Patients may choose not to enter the long term extension, in which case the Investigator will decide whether the patient should discontinue high dose of donepezil without down-titration, or whether donepezil should be downtitrated to their own standard of donepezil dose. Whatever the decision, the patient will be treated at least an additional 7 days with solifenacin 15 mg/day.

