3.2 Dose Escalation and Stopping rules

For all patients, donepezil dose escalation will be discontinued if they manifest over a 24 hour period after study drug administration the following symptoms judged by the investigator as possibly or probably study-drug related:

- One (1) episode of vomiting, or
- Two (2) episodes of severe retching (separated by more than one hour on the same day), or
- One (1) episode of severe nausea (Grade 3; defined as nausea interfering with activities of daily living or inadequate oral caloric or fluid intake; tube feeding, total parenteral nutrition or hospitalization indicated) and/or severe abdominal discomfort (Grade 3; defined as severely interfering with activities of daily living), or
- Three (3) episodes of moderate nausea (Grade 2; defined as subjectively symptomatic, but not interfering with activities of daily living) and/or moderate abdominal discomfort (Grade 2; defined as interfering with function, but not interfering with activities of daily living) each on the same day, or
- One (1) episode of moderate diarrhea (Grade 2; defined as 4 to 6 stools more than at baseline).
- Any other circumstance that merits an adjustment in study drug dosage in the opinion of the investigator

All those meeting one or more of the foregoing stopping rules will be withdrawn from dose titration and proceed in accordance with either of the two options given above.

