3.5.2 Discontinuation of individual subjects from the entire study

During the study, the investigator or the sponsor may decide to discontinue a subject's participation in the study in the following cases:

- A protocol violation occurs;
- A serious or intolerable (other than those listed in the discontinuation of rivastigmine escalation criteria) AE occurs;
- The Sponsor or Investigator terminates the study.
- The subject requests to be discontinued from the study.
- The subject is non-compliant to any part of the study.
- The Investigator feels it is not in the best interest of the subject to continue in the study.

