4.2 Exclusion criteria

The criteria for exclusion of a subject from enrollment in the study are as follows:

- 1. Women of child bearing potential.
- 2. History or presence of a seizure disorder.
- 3. Current unstable peptic ulcer disease, urinary or gastric retention; asthma or obstructive pulmonary disease.
- 4. History or presence of bladder outflow obstruction, gastrointestinal obstructive disorder or reduced GI motility, or narrow-angle glaucoma.
- 5. History or presence of gastrointestinal, hepatic, or renal disease, or other condition known to interfere with the absorption, distribution, metabolism or excretion of drugs.
- 6. Renal and hepatic dysfunction with:
 - Total Bilirubin: >1.5 x UNL
 - AST: >2.5 x UNL

- ALT: >2.5 x UNL
- Serum Creatinine: >1.5 x UNL
- Creatinine Clearance: <30 mL/min
- 7. History or presence of myasthenia.
- 8. History or family history of Prolonged QT Syndrome.
- 9. History of unexplained syncope or family history of unexplained syncope or sudden death.
- 10. Myocardial infarction or hospitalization for congestive heart failure within 6 months.
- 11. ECG findings of:
 - Complete Left Bundle Branch Block;
 - Ventricular pacing;
 - 2nd degree or 3rd degree AV block;
 - Atrial fibrillation or atrial flutter;
 - HR <45 or >100;
 - PR >220 msec; or
 - QTcF >450 msec in male, >470 msec in female
- 12. Known hypersensitivity to donepezil, solifenacin or related drugs.
- 13. History of drug significant allergy.
- 14. History of substance abuse, known drug addiction, or positive test for drugs of abuse or alcohol.
- 15. Patients treated with the following medications within 8 weeks of screening
 - AChEIs (other than donepezil),
 - Peripherally acting anticholinergics (such as drugs for the treatment of overactive bladder disorder),
 - Psychoactive medications (including antipsychotics, antidepressants, anxiolytics or sedative hypnotics) having significant anticholinergic effects and/or believed to affect cognitive function.

Other medications are acceptable, at the investigators discretion, if dosage is held stable for at least 4 weeks prior to screening and throughout the study.

- 16. Patients considered unlikely to co-operate in the study, and/or poor compliance anticipated by the investigator.
- 17. Patients hospitalized within 4 weeks of screening.

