7.6 Vital signs and body weight

Vital signs, including blood pressure, heart rate, respiratory rate, and temperature, will be measured after the patient rests in the supine position for at least 5 minutes.

Body weight will be measured as indicated in Table 1-4.

7.7 12-Lead ECGs

A standard 12-lead ECG will be recorded as indicated in Table 1-4. The Investigator will evaluate the ECG results as normal, abnormal, not clinically significant, or abnormal, clinically significant.

If QTcF on an on treatment ECG is \geq 500 msec then hold treatment and perform 3 repeat ECGs over 20-60 min; if the mean QTcF of the three ECGs is \geq 500 msec, withhold treatment and perform a repeat ECG the following day; if the QTcF has returned to baseline, dosing may resume.

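### Section 3.5.2 separates titration stops from study discontinuations by a rivastigmine list absent from the available protocol, so the same intolerable AE can take either route

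*Protocol*

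**What the plan says.** Protocol 3.2 lists named gastrointestinal stopping symptoms and ends with a catch-all: "Any other circumstance that merits an adjustment in study drug dosage in the opinion of the investigator". It then disposes of every such patient: "All those meeting one or more of the foregoing stopping rules will be withdrawn from dose titration", and they are to "proceed in accordance with either of the two options given above".

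The two options are in Protocol 3.1. Option 1 is immediate entry to the extension at the MTD or the maximum allowed dose. Option 2 is for patients who decline the extension. The investigator chooses between stopping high-dose donepezil outright and down-titrating it, and the text adds: "Whatever the decision, the patient will be treated at least an additional 7 days with solifenacin 15 mg/day".

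Protocol 3.5.1, headed for donepezil, repeats the 3.2 list, catch-all included. Protocol 3.5.2 then says the investigator or sponsor may discontinue a subject from the entire study in several cases. One of them reads: "A serious or intolerable (other than those listed in the discontinuation of rivastigmine escalation criteria) AE occurs". Others are the subject's own request and the investigator's view of the subject's best interest.

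SAP 2.4.1 makes each patient's FID and MTD the primary measures. SAP 6.2 bases the primary summary on subjects who completed donepezil titration. SAP 8.1.1 counts separately those who discontinued before completing it.

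**The concern.** The exception in 3.5.2 is the only wording that separates an AE that ends dose escalation from an AE that ends participation. It points to criteria for a different drug. Outside that clause, rivastigmine appears only in the reference list of the available text. A site therefore cannot tell from the protocol which section governs a given intolerable AE.

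Two things depend on the route. The first is what happens to the patient: 3.2 leads to the extension or to continued solifenacin, while 3.5.2 allows exit from the study. The second is the trial's result. A titration stop yields an FID and an MTD. A study discontinuation may be counted as titration not completed, which would take an intolerant patient out of the primary summary. In a study whose purpose is to choose a titration schedule on tolerability, losing such patients from the summary makes the schedule look better tolerated than it was.

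**Working it through.** The plan states no figure to reproduce. The check sets the sections side by side under each way of reading the rivastigmine clause, and then sizes one patient.

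**Force of each section.** Section 3.2 is mandatory and covers everyone who meets any rule. Section 3.5.2 is permissive. Neither refers to the other, and neither says which prevails.

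**Three readings of the clause**

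1. *Literal.* No rivastigmine criteria exist in the available text, so the exception removes nothing. Any serious or intolerable AE qualifies for 3.5.2. A listed gastrointestinal symptom judged intolerable meets both 3.2 and 3.5.2.
2. *Donepezil meant, catch-all counted as listed.* Any AE that merits a dose adjustment is then excepted, so the AE case in 3.5.2 is left with little of its own. The best-interest and subject-request cases still allow exit, beside a mandatory 3.2 route.
3. *Donepezil meant, catch-all not counted as a listed AE.* Gastrointestinal symptoms go to 3.2, and other intolerable AEs may go to 3.5.2. Those other AEs still meet the 3.2 catch-all whenever the investigator thinks the dose should change, so they again have two routes.

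Each reading leaves some class of intolerable AE with two permitted routes.

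**Link to the analysis.** A patient on the 3.2 route has reached an FID. Because SAP 6.2 serves a summary of FID and MTD, I assume that reaching the FID counts as completing titration, although the SAP does not define completion. A patient on the 3.5.2 route could be placed among those who discontinued before completion (SAP 8.1.1), and so outside the SAP 6.2 population.

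**Size of one patient**

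- Planned evaluable subjects per group per cohort: n = 4 to 6 (Protocol Summary, sample size; SAP 3).
- Share of a cell: 1/n. For n = 4, 1/4 = 25%. For n = 6, 1/6 = 16.7%.
- For the enrolled counts in SAP 2.1: Cohort 1, 1/8 = 12.5%; Cohort 1b, 1/6 = 16.7%.
- Effect on the proportion tolerating the highest dose (SAP 8.2). Let x of n tolerate it, and let one intolerant patient leave the population. The proportion goes from x/n to x/(n−1), a rise of x/[n(n−1)].
  - Assumed example with half tolerating: n = 6, x = 3 gives 3/30 = 10 points (50% to 60%); n = 4, x = 2 gives 2/12 = 16.7 points (50% to 66.7%).
  - The largest rise is at x = n−1 and equals 1/n: 16.7 points for n = 6 and 25 points for n = 4.

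The change is never downward, because the patient who leaves is always one who did not tolerate the dose.

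**The case against.** The best reply is that the rivastigmine reference is a plain carry-over. Read as donepezil, it gives a sensible division: listed gastrointestinal symptoms stop escalation, and other serious or intolerable AEs may end participation. That is a natural reading and probably the intended one. It does not close the gap, because the catch-all also stands in 3.2 and its routing is mandatory.

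A second reply is that the result is already protected. Protocol 7.3 requires each patient's FID to be recorded, Protocol 9.1.1 presents MTD and FID for each patient, and the SAP lists dose-limiting side effects (8.2) and summarises discontinuation reasons (8.1.1). This stands for the listings. It does not settle who is in the SAP 6.2 population for the primary summary.

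Third, the visit procedures under 3.3.2 and the whole of 3.4 are absent from the public text and may deal with early termination. That limits the statement to the text available.

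Some readers may infer more than the documents support:

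- *That a patient stopped for a reaction to solifenacin must be given more of it.* Section 4.2 excludes patients with "Known hypersensitivity to donepezil, solifenacin or related drugs" at entry, which makes the inference tempting. But 3.5.2 lets a patient leave on request or in the patient's best interest, and neither case carries the rivastigmine exception. In Option 2, the decision referred to is the choice about donepezil down-titration, not the reason for stopping.
- *That Option 2 contradicts the QTcF rule in 7.7*, which says to "withhold treatment and perform a repeat ECG the following day". Nothing in 7.7 places such a patient under a stopping rule or in Option 2, so the conflict is not shown.
- *That both options expressly continue solifenacin.* Only Option 2 names it. For Option 1 it is inferred from the definition of CPC-201 as the combination.

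**Conclusion.** The point holds as a defect in operative text. A mandatory route in 3.2 and a permitted exit in 3.5.2 overlap, the clause meant to separate them refers to criteria not in the available protocol, and no precedence is stated. It is more than clerical, because the route can decide whether an intolerant patient enters the FID and MTD summary.

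One such patient is 16.7% to 25% of a planned cell. Leaving that patient out raises the proportion tolerating the highest dose by at most the same number of points. This rests on two assumptions: that at least one patient is routed under 3.5.2 for intolerability, and that such a patient is treated as not having completed titration. The documents report no such case. The finding is about ambiguity with a possible upward bias, not a demonstrated error in the result, and it does not show that any patient is obliged to stay on solifenacin.

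**What to change.** - **Protocol 3.5.2:** replace the rivastigmine reference with the section actually meant.
- **Protocol 3.1 (Option 2), 3.2, 3.5.1 and 3.5.2:** reconcile them. State which section prevails when an AE meets both 3.2 and 3.5.2, and whether the Option 2 solifenacin sentence applies to a patient discontinued under 3.5.2. The clinical content is for the sponsor to settle.
- **SAP 6.2:** state that a subject who stops for intolerability is counted in the FID and MTD summary whichever route was used, and define completion of titration accordingly.

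The cost is wording only: a protocol amendment or site clarification letter and one sentence in the SAP, with no new procedures or data. If enrolment has closed, the SAP sentence, or the same rule stated in the study report, still resolves the analysis part.

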3.2 Dose Escalation and Stopping rules

For all patients, donepezil dose escalation will be discontinued if they manifest over a 24 hour period after study drug administration the following symptoms judged by the investigator as possibly or probably study-drug related:

- One (1) episode of vomiting, or
- Two (2) episodes of severe retching (separated by more than one hour on the same day), or
- One (1) episode of severe nausea (Grade 3; defined as nausea interfering with activities of daily living or inadequate oral caloric or fluid intake; tube feeding, total parenteral nutrition or hospitalization indicated) and/or severe abdominal discomfort (Grade 3; defined as severely interfering with activities of daily living), or
- Three (3) episodes of moderate nausea (Grade 2; defined as subjectively symptomatic, but not interfering with activities of daily living) and/or moderate abdominal discomfort (Grade 2; defined as interfering with function, but not interfering with activities of daily living) each on the same day, or
- One (1) episode of moderate diarrhea (Grade 2; defined as 4 to 6 stools more than at baseline).
- Any other circumstance that merits an adjustment in study drug dosage in the opinion of the investigator

All those meeting one or more of the foregoing stopping rules will be withdrawn from dose titration and proceed in accordance with either of the two options given above.

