7 SAFETY ASSESSMENTS

7.1 Adverse Events

An AE is any untoward medical occurrence in a patient or clinical-investigation subject administered a pharmaceutical product that does not necessarily have a causal relationship with this treatment. A TEAE is defined as any AE that occurs after administration of the first dose of study drug. An AE can therefore be an unfavorable and unintended sign (including an abnormal laboratory finding), symptom, or disease temporally associated with the use of a medicinal (investigational) product, whether or not related to the medicinal (investigational) product. The failure of the anticipated pharmaceutical action of an investigational drug does not constitute a related AE.

AE rating

The condition of the subjects will be closely monitored throughout the study. The investigator will collect the AEs reported spontaneously, observed, or elicited in response to a non-leading question (for example, "How have you been feeling since we last asked you?"). The investigator will record all AEs in the source records and the CRF.

• The intensity/severity of an AE will be rated as follows:

Mild	: Awareness of signs or symptoms, but no disruption of usual activity.
Moderate	: Event sufficient to affect usual activity (disturbing).
Severe	: Inability to work or perform usual activities (unacceptable).

- The causal relationship of an AE to the study drugs will be rated as follows:
 - Not related : Temporal relationship of the onset of the event, relative to the administration of the product, is not reasonable or another cause can by itself explain the occurrence of the event
 - Unlikely : Is general, this category can be considered applicable to those AEs

related	which after careful medical consideration at the time they are
	evaluated, are judged to be unrelated to the study drug
Related	: AEs incontrovertibly related to the administration of the product.

Of the above definitions, AEs related to study drug are considered adverse reactions, while "unlikely" and "not related" do not represent a causal relationship.

- The action taken with the study drug for an AE will be rated as product withdrawn, not changed, not applicable. AEs requiring therapy will be treated with recognised standards of medical care to protect the health and the well-being of the subject.

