9.1.2 Adverse Events

Data Listings will present the verbatim-reported event along with the preferred term and SOC, onset and stop dates, severity, relatedness, SAE status, action taken and outcome. For summaries by severity, the most severe event episode will be counted if a subject has more than one event within the same coded term. For summaries of treatment-associated events, the subject will be counted as "associated" for that term if a subject has more than one event within the same coded term or if one event is considered "not associated" and the other "associated".

Unless otherwise indicated, AE summary tables will be presented by study period, treatment group, SOC, and preferred term for each study period.

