8.3.1.1 Adverse Events

Adverse events will be classified by system organ class (SOC) and preferred term (PT) according to the most recent version of MedDRA dictionary.

TEAE are defined as events with an onset on or after administration of the first dose of study drug. TEAEs will be summarized, System Organ Class, and preferred term. The following TEAE summaries will be provided:

- Top line summary table including
 - all treatment emergent Adverse Events (TEAEs), treatment related TEAE and treatment unrelated TEAE,
 - Serious treatment emergent Adverse Events (STEAEs), treatment related STEAE and treatment unrelated STEAE
 - Deaths
- Overall (*i.e.*, regardless of severity or relationship to treatment)
- By cohort (*i.e.*, 1, 2, 1b, 3c)
- By study phase (*i.e.*, titration and long term extension)
- By severity grade (mild, moderate, severe)
- By relationship to study drug (definitely, probably, possibly, not related)

Unless otherwise specified, at each level of subject summarization, a subject will be counted only once. If there is more than one occurrence of an event, the event of the worst severity or the worst-case relationship category will be summarized.

Serious Adverse Events (SAEs) will also be summarized by relationship.

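### Protocol 7.1 has no causal level for an event judged possibly or probably drug-related, and ratings on its scale cannot fill the relationship summaries in SAP 8.3.1.1

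*Protocol*

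**What the plan says.** Four places deal with causality.

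- **Protocol 3.2 and 3.5.1 (stopping titration).** Escalation ends for listed gastrointestinal "symptoms judged by the investigator as possibly or probably study-drug related". A final catch-all bullet leaves other cases to the investigator.
- **Protocol 7.1 (rating adverse events).** There are three levels. *Not related* covers implausible timing or another sufficient cause. *Unlikely related* covers events that "are judged to be unrelated to the study drug". *Related* covers "AEs incontrovertibly related to the administration of the product". Only the last counts as an adverse reaction; the other two "do not represent a causal relationship".
- **Protocol 9.1.2 (summaries).** The terms become *associated* and *not associated*. A subject counts as associated "for that term if a subject has more than one event within the same coded term", or if one event is rated associated and another is not.
- **SAP 8.3.1.1 (analysis).** The top-line table shows "treatment related TEAE and treatment unrelated TEAE", with the same split for serious events. A further summary is "By relationship to study drug (definitely, probably, possibly, not related". For repeated events, "the event of the worst severity or the worst-case relationship category will be summarized".

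The stopping wording and the 7.1 scale are the same in all three protocol versions supplied. SAP section 1 lists the July 2016 protocol among the documents reviewed.

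**The concern.** The stopping rule and the SAP both work with degrees of likelihood. The scale in 7.1 jumps from judged unrelated to beyond dispute. Most drug-attributed symptoms in a titration study fall between those poles, and that middle ground is where the stopping rule operates.

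An investigator who follows 7.1 as written must push such an event down to *unlikely related* or up to *related*, and sites may choose differently. The programmer then receives three levels and has to produce four. The SAP gives no mapping, so one would have to be made up, possibly with the data in view.

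At stake are the relationship summaries of TEAEs and serious TEAEs. They serve the secondary objective, safety and tolerability by dose and titration rate, and SAP 8.3.1 promises to analyse these data by dose and titration schedule.

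**Working it through.** The plan gives no figure to reproduce, so the main check compares labels.

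**1. The level sets**

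| Source | Levels |
|---|---|
| Protocol 3.2/3.5.1 | possibly, probably |
| Protocol 7.1 | not related, unlikely related, related |
| SAP 8.3.1.1 | definitely, probably, possibly, not related |

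**2. Shared labels**

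- 3.2/3.5.1 and 7.1: none.
- 7.1 and SAP: one (*not related*).
- 3.2/3.5.1 and SAP: two (*possibly*, *probably*).

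**3. Can 7.1 ratings fill the SAP table?** *Not related* carries over. *Related*, defined as beyond dispute, fits *definitely* at best. *Unlikely related* has no row. Nothing in 7.1 supplies *probably* or *possibly*. Three levels cannot be expanded to four without information that was not collected.

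**4. One case followed through.** A patient vomits once and the investigator thinks the drug probably caused it. Under 3.2 titration stops. Under 7.1 the event is not beyond dispute, yet it was not judged unrelated either, so no level fits.

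- Rated *unlikely related*, it falls on the unrelated side. The related proportion is then too low if related is meant to include probable events.
- Rated *related*, it overstates certainty. It is too high by 7.1's own definition, and too high in the *definitely* row if it is placed there.

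The text forces neither choice.

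**5. If the CRF used the SAP's four levels.** The table can be filled. What remains is that the SAP does not state which levels make up treatment related, and that 7.1 describes a scale not in use. If possibly and probably are counted as related, the numerical effect is zero.

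**6. What one subject is worth.** SAP 2.1 gives 8 subjects in Cohort 1 and 1 in Cohort 2 at the first amendment, and 6 in Cohort 1b at the second. No enrolled number is given for Cohort 3c. I assume 6 (Group 1 only) to 12 (both groups at about 6 each), and that everyone enrolled was dosed. One subject with no other related TEAE who changes side moves the proportion by:

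- Cohort 1: 1/8 = 12.5 points
- Cohort 1b: 1/6 = 16.7 points
- Cohort 3c: 1/6 = 16.7 to 1/12 = 8.3 points
- Pooled: 8 + 1 + 6 = 15, plus 6 to 12, gives 21 to 27; 1/21 = 4.8 to 1/27 = 3.7 points

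These figures show only how coarse tables of this size are. They do not estimate the defect, because the number of affected subjects is unknown and may be 0.

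**The case against.** The best reply is that the harm depends on a CRF that is not in the documents. The SAP shares *possibly* and *probably* with the stopping rule, so a four-level CRF is at least as consistent with the text as a three-level one. Also, 7.1 does draw a causal line on its own scale, and the SAP's only non-causal level is *not related*, so the natural reading leaves the other three as related. All of this stands. It makes the numerical consequence conditional and narrows the missing definition to the SAP's term. It does not repair 7.1, which gives a possible or probable event nowhere to go.

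A reader might also infer stronger claims that the documents do not support:

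- *Escalation could continue after a definitely related symptom, since 3.2 does not name that level.* The wording reads naturally as a minimum threshold, and the catch-all bullet covers the case.
- *The primary outcome is compromised.* FID, MTD and highest dose reached follow from the stopping decision and the doses taken, not from the relatedness rating.
- *SAP 7.3 forbids a recode by saying that data are used as observed.* That is a missing-data rule and does not address category mapping.
- *Protocol 9.1.2 will inflate the counts.* Read literally, it makes any two events in one coded term associated. The SAP's worst-case rule governs the analysis, so this is a drafting slip.

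**Conclusion.** The point holds, as a minor one. Protocol 7.1 cannot record the causal judgement on which the stopping rule depends, and the SAP's relationship summaries cannot be produced from ratings on the 7.1 scale without a mapping that appears nowhere in the visible text. Which levels count as treatment related is left unsaid on either CRF assumption.

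The effect is confined to descriptive, secondary TEAE summaries. Its size is unknown, its direction could be either way, and it may be zero. It arises only if ratings were made on the 7.1 scale and the affected subject has no other related TEAE. The dose-limiting side effect listing does not change, and by-subject AE listings that include relatedness, as protocol 9.1.2 requires, would let a reader see any discordance. It does not follow that the reported tables are wrong.

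**What to change.** - **(a) Protocol 7.1.** For events still to be rated, use the SAP's four levels. If none remain, the other steps carry the fix.
- **(b) SAP 8.3.1.1.** Define treatment related as possibly, probably or definitely related.
- **(c) Ratings already made on the 7.1 scale, if any.** Tabulate them separately on their own three levels, with *related* as treatment related. Do not compare related proportions across schedules rated on different scales without a footnote, because the threshold differs: beyond dispute on one scale, possible on the other.
- **(d) Consistency check.** Compare each symptom-based titration stop (the gastrointestinal bullets, not the catch-all) with the relatedness rating of the matching event. Query the site where they disagree, recode nothing automatically, and footnote cases that stay discordant.
- **Optional.** In protocol 9.1.2, delete the clause that makes repeated events in one coded term *associated*.

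The cost is a small wording amendment, a few SAP sentences, one check and perhaps a few site queries. Protocol 3.1 says Cohorts 1 and 2 were complete before the July 2016 amendment, so a new scale cannot reach their ratings. If both scales were used, the report must show them side by side, which is less tidy but keeps the investigators' ratings as made.
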